2.7 Safety evaluation

All safety evaluation will be based on the safety set.

The study will be reviewed for safety issues by an independent, external data safety monitoring board (DMC), as described in [Section 2.9 Interim analysis](#).

2.7.1 Serious asthma outcomes

A composite endpoint of serious asthma outcomes is defined as a) asthma-related hospitalization, b) asthma-related intubation, or c) asthma-related death. All serious asthma outcomes and deaths occurring from the time of randomization until the 30 days after permanent discontinuation of study drug will be adjudicated by an independent external committee to determine their asthma relatedness.

The composite endpoint as well as each single component of it will be analyzed for the number of patients with the event. If a sufficient number of events ($\geq 10\%$ of patients) occurs, the composite endpoint and its components will be also analyzed for the time to event and the annual rate of events; similar inferential analyses as described for asthma exacerbations will be performed.

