Furthermore, as additional secondary objectives, QMF149 150/320 µg o.d. delivered via Concept1 will be compared with salmeterol xinafoate /fluticasone propionate 50/500 µg via Accuhaler® for all the listed secondary endpoints above as well as the following ones:

- Trough FEV₁ measured after 26 weeks of treatment
Trough FEV₁ will be tested for non-inferiority versus salmeterol/fluticasone 50/500 µg. If non-inferiority criteria are met, this will be tested for superiority.
- Asthma control as assessed by the ACQ-7 after 26 weeks treatment.

The following safety and tolerability endpoints will be evaluated for all treatment comparison groups:

- Cumulative incidence of the composite endpoint of serious asthma outcomes (i.e. asthma-related hospitalization, asthma-related intubation, or asthma-related death) over 52 weeks of treatment
- Adverse events, vital signs, ECG and laboratory analysis (hematology, blood chemistry including glucose and potassium, urinalysis, evening plasma cortisol) over 52 weeks of treatment

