Time-to-event variables will be analyzed using a Cox regression model stratified by age (12 to 17, ≥ 18 years). The model will include treatment, region and history of asthma exacerbation in the 12 months prior to screening (Yes, No) as fixed-effect factors, and FEV₁ prior to inhalation and FEV₁ 15 to 30 min post inhalation of salbutamol/albuterol (components of SABA reversibility) as covariates. For treatment comparisons the estimated adjusted hazard ratio will be displayed along with the associated two-sided 95% confidence interval and corresponding p-value. Kaplan-Meier analysis stratified by treatment group will be also presented and displayed graphically. Patients without an event will be considered as censored at the earliest date of (last treatment + 1, death, last visit). In the interim analysis, patients without an event who are ongoing at the time of interim database freeze will be censored at the DLP. For patients having an event, the start date of the exacerbation will be considered to calculate the time to event (i.e., the number of days from start of treatment up to the event start date).

Time to first hospitalization for asthma exacerbation (only for severe exacerbations possible)

The analysis is similar to time to first asthma exacerbation.

Time to permanent discontinuation of study drug due to asthma exacerbation

The analysis is similar to time to first asthma exacerbation.

Duration of asthma exacerbations in days, by exacerbation category

The duration of asthma exacerbations is defined as the sum of days per patient over all exacerbations and the respective lengths (from start to end date). This will be analyzed for treatment group differences using the van Elteren test stratified for age (12 to 17, or ≥ 18), region and history of asthma exacerbation in the 12 months prior to screening (Yes, No).

Total amounts (in doses) of oral corticosteroids used to treat asthma exacerbations

Total amount (in prednisone-equivalent mg doses) of oral corticosteroid used to treat asthma exacerbations during the 52 week treatment period will be summarized descriptively by treatment group.

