To control for possible differences in exposure between the treatment groups, AEs will also be presented with incidence rates per 100 patient-years, for first onset of event where the exposure is only counted up to the time of the first event. The incidence rate per 100 patient years will be calculated as $100 \times (\text{the total number of patients with the event of interest} / \text{the total number of exposure in patient-years})$. In the denominator, patients with the event of interest will be counted up to the time of the first event while patients without the event of interest will be counted with their full exposure (see Section 2.4.1 for the definition of exposure). Total patient years will be computed as sum of days of exposure over all patients divided by 365.25).

The Compound Case Retrieval Strategy will be used to determine the MedDRA search criteria to be used to identify events of special interest. The most recent list of adverse events of special interest at the time of database lock will be used.

Adverse events of special interest and SAEs of special interest will be presented by risk and preferred term and will also be analyzed for the following selected subgroups:

- Age group (12 to 17 years, \geq 18 years)
- Sex (male, female)
- Pre-bronchodilator FEV₁ in % of predicted FEV₁ at run-in visit 101 (50% to < 60%, 60% to < 85%)

All deaths in the clinical database will be listed with both the investigator-reported principal cause and the adjudicated primary cause presented side by side. If adverse events (including asthma exacerbations) leading to death start between the first dose and the last dose + 30 days, then those deaths will be included in summary tables. The adjudicated primary cause of death will be summarized with pre-defined categories (cardiovascular, respiratory, cancer, other, intermediate causes) and subcategory.

In addition, time to event analyses will be done for the following endpoints:

- adverse event by the 5 most frequent preferred terms,
- serious adverse event (if there are more than 10% of patients with at least one SAE)
- adverse event of special interest by risk category (if there are more than 10% of patients with events in the respective risk category)
- adjudicated serious asthma outcome (composite endpoint and by single component – if there are more than 10% of patients with events)

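### The plan guarantees only a count for the adjudicated serious-asthma composite; a censoring-adjusted 52-week cumulative incidence depends on a 10% threshold that is worded two ways and has no stated denominator

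*SAP*

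**What the plan says.** SAP 2.1.3, matching protocol 2.3, lists among the safety endpoints: "Cumulative incidence of the composite endpoint of serious asthma outcomes (i.e. asthma-related hospitalization, asthma-related intubation, or asthma-related death) over 52 weeks of treatment". SAP 2.7.1 has an independent external committee adjudicate these outcomes from randomisation until 30 days after study drug is stopped for good.

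The analysis in SAP 2.7.1 has two tiers.

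- Always done: "The composite endpoint as well as each single component of it will be analyzed for the number of patients with the event".
- Conditional: "If a sufficient number of events ($\geq 10\%$ of patients) occurs", then "the composite endpoint and its components will be also analyzed for the time to event and the annual rate of events", by methods similar to those for exacerbations.

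SAP 2.7.2 lists time to adjudicated serious asthma outcome again, for the composite and by single component, with the condition "if there are more than 10% of patients with events".

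SAP 2.6.2.7 plans an annual-rate model for severe exacerbations, and Cox models for time to first severe exacerbation and to first hospitalisation for an exacerbation, with no event threshold. It adds: "Kaplan-Meier analysis stratified by treatment group will be also presented and displayed graphically".

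**The concern.** A count of patients does not estimate a 52-week cumulative incidence when patients are followed for different lengths of time. Dropout causes this in the full study report. In the first report it is built in, because patients still on treatment have between 26 and 52 weeks of exposure (protocol 3.5).

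The SAP accepts this reasoning elsewhere. SAP 2.1.5 drops logistic regression for exacerbation percentages because time-to-event methods account for censoring. SAP 2.7.2 adds patient-year rates for adverse events to allow for differences in exposure. The composite that goes to an adjudication committee is the one left with a count.

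The threshold is also loosely specified. Neither section says whether 10% refers to all patients, to one arm or to one component. In 2.7.1 a sufficient number of events seems to release the composite and its components together; 2.7.2 can be read as testing each component separately. The choice could be made after the counts are known.

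At stake is how well the report describes the most serious asthma events in a trial of a LABA combination. Protocol 3.6 records the class concern about severe exacerbations with LABA used alone, while noting that LABA is given here only with an ICS.

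**Working it through.** The plan gives no expected event rate or target precision for this endpoint, so it has no figure of its own to reproduce. True risks below are assumptions, shown as a range.

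**Inputs.** 2000 patients, 400 per arm, five equal arms, 10% dropout (protocol 3.1 and 9.8, SAP 2.10). Threshold 10% (SAP 2.7.1 and 2.7.2). Follow-up of 26 to 52 weeks in the first report (protocol 3.5).

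**1. Size of the threshold.** Overall: 0.10 × 2000 = 200 patients, or 201 if the condition is more than 10%. One arm: 0.10 × 400 = 40, or 41.

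**2. Chance of meeting it.** Exact binomial with the same true risk p in every arm: P(X ≥ 200) with X ~ Bin(2000, p) for the overall reading; q = P(X ≥ 40) with X ~ Bin(400, p) for one given arm; 1 − (1 − q)^5 for at least one of five arms.

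| True risk | Overall | One given arm | At least one arm |
|---|---|---|---|
| 5% | 6 × 10^-20 | 0.003% | 0.02% |
| 7% | 4 × 10^-7 | 1.5% | 7.5% |
| 8% | 0.08% | 8.7% | 36% |
| 9% | 6.5% | 27% | 79% |
| 10% | 51% | 52% | 98% |

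The overall and at-least-one-arm readings diverge sharply from 7% upward, so the missing denominator matters.

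**3. Bias of the crude proportion under dropout.** Assume a constant event hazard λ and dropout hazard μ, in years. The expected crude proportion is λ/(λ + μ) × [1 − exp(−(λ + μ))]. For a true 52-week risk of 2.0%, λ = −ln(0.98) = 0.0202. For 10% dropout over the year, μ = −ln(0.90) = 0.1054. Then 0.0202/0.1256 × (1 − 0.98 × 0.90) = 0.1609 × 0.118 = 1.90%, about 5% low in relative terms. With 20% dropout it is 1.79%, about 10% low. The relative shortfall is nearly the same at true risks of 1% and 5%.

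**4. The first report.** Assume follow-up uniform over 0.5 to 1 year and no dropout. The expected crude proportion is 1 − [exp(−λ/2) − exp(−λ)]/(λ/2) = 1 − (0.98995 − 0.98000)/0.01010 = 1.5%, against a true 52-week risk of 2.0%.

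**5. Is an estimate useful with few events?** Exact (Clopper-Pearson) 95% intervals:

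- 4/400: 1.0% (0.3 to 2.5%)
- 8/400: 2.0% (0.9 to 3.9%)
- 20/400: 5.0% (3.1 to 7.6%)
- 40/2000: 2.0% (1.4 to 2.7%)

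The intervals are wide, but they still bound the risk.

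**6. Is a comparative model useful?** Schoenfeld power for a hazard ratio of 2 with D events over two equal arms is Φ(ln 2 × √(D/4) − 1.96). For D = 16: Φ(0.693 × 2 − 1.96) = Φ(−0.57) = 28%. For D = 8: 16%. The Cox model in SAP 2.6.2.7 has about 12 parameters (treatment 4, region 5, exacerbation history 1, FEV1 covariates 2). A minimum event number for the models is reasonable; the descriptive estimate does not need one.

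**The case against.** The strongest reply is that little is lost. The unconditional count, divided by the safety-set size, gives a crude incidence per arm, and neither document says that cumulative incidence must mean Kaplan-Meier. Severe exacerbations, whose definition in protocol 6.4.5 includes asthma hospitalisation and death, have rate, Cox and Kaplan-Meier analyses without a threshold. So does first hospitalisation for an exacerbation. Serious adverse events are summarised with exposure-adjusted rates (SAP 2.7.2), and the monitoring committee reviews all deaths and hospitalisations. The bias in the full report is small, and it affects between-arm comparisons little unless dropout differs by arm. The difference between at least and more than 10% is a single patient.

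Much of this stands. A reader might infer that the endpoint will never be estimated, or that analysis of severe asthma events is switched off. The documents support neither reading: a crude proportion is always available, and closely related events are fully analysed.

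Those related analyses still do not replace the composite. SAP 2.6.2.7 works from the exacerbation eCRF without adjudication, on the full analysis set, with events up to one day after the last dose. The composite is adjudicated, analysed on the safety set, and adjudicated through 30 days after discontinuation. The serious adverse event tables are organised by system organ class and preferred term.

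Nor should the threshold be replaced by a very low event count for the Cox and rate models. Ten events over two arms, for instance, would be too few for a model of this size.

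**Conclusion.** The point holds in a limited form. For the adjudicated composite the plan guarantees a count, and it makes the censoring-adjusted 52-week incidence, the annual rate and the formal comparison depend on an imprecise 10% condition. If the true risk is about 7% or less and the 10% is taken over all patients, those analyses will almost surely not be produced. Both conditions are assumptions: the documents state neither an event rate nor a denominator, and if one arm reaching 10% is enough, the chance rises to 7.5% at a true 7% and 36% at 8%.

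The remaining crude proportion is biased low by about 5% relative under 10% dropout, and more in the first report (2.0% appearing as about 1.5%). These figures assume constant hazards and, for the first report, uniform follow-up.

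This is a descriptive safety endpoint outside the multiplicity family (SAP 2.6.1.3), so no confirmatory conclusion is affected. Parts of protocol 9.5.2 are not visible in the text reviewed, and no omission is claimed there. It is a low-cost improvement worth making.

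**What to change.** In SAP 2.7.1, report for every arm, with no threshold, the Kaplan-Meier cumulative incidence of the adjudicated composite at Week 52 with a 95% CI, and at Week 26 in the first report. Add an exposure-adjusted incidence rate. The censoring rule already in SAP 2.7.2, including the data-lock date for ongoing patients, can be used as it stands.

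Keep a threshold only for the Cox and negative binomial models. Word it identically in 2.7.1 and 2.7.2, and state whether it applies to all patients, to each arm or to the arms compared, and whether it is assessed for the composite or for each component.

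The cost is a few sentences in the SAP and a few extra safety tables. Intervals will be wide when events are few.

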2.7.2 Adverse events

All adverse events (AEs) including asthma exacerbations, coded with MedDRA using the most actual version at the time of database lock, will be listed. In general, summaries will include treatment-emergent adverse events only, i.e., those starting on or after the time of the first administration of study drug but not later than 7 days (30 days in the case of a serious adverse event, SAE) after the last administration.

The number, percentage, and exposure-adjusted rate of patients who reported treatment-emergent adverse events will be summarized by primary system organ class, preferred term, and treatment for

- all adverse events
- all adverse events by maximum severity
- adverse events suspected to be related to study drug
- all adverse events with time at onset ≤ 26 weeks
- adverse events leading to permanent study drug discontinuation
- all adverse events by standardized MedDRA query (SMQ) level, and by SMQ level and preferred term
- serious adverse events
- serious adverse events suspected to be related to drug
- serious adverse events leading to permanent study drug discontinuation
- fatal adverse events
- adverse events of special interest (by risk and preferred term)
- serious adverse events of special interest (by risk and preferred term)

Unless otherwise specified, primary system organ classes will be sorted alphabetically and, within each primary system organ class, the preferred terms will be sorted in descending order

of frequency in the QMF149 150/320 µg treatment group. If a patient reported more than one adverse event with the same preferred term, the adverse event will be counted only once. If a patient reported more than one adverse event within the same primary system organ class, the patient will be counted only once at the system organ class level.

In addition, the most frequent adverse events will be presented by preferred term in descending order of frequency in the QMF149 150/320 µg treatment group.

To control for possible differences in exposure between the treatment groups, AEs will also be presented with incidence rates per 100 patient-years, for first onset of event where the exposure is only counted up to the time of the first event. The incidence rate per 100 patient years will be calculated as $100 \times (\text{the total number of patients with the event of interest} / \text{the total number of exposure in patient-years})$. In the denominator, patients with the event of interest will be counted up to the time of the first event while patients without the event of interest will be counted with their full exposure (see Section 2.4.1 for the definition of exposure). Total patient years will be computed as sum of days of exposure over all patients divided by 365.25).

The Compound Case Retrieval Strategy will be used to determine the MedDRA search criteria to be used to identify events of special interest. The most recent list of adverse events of special interest at the time of database lock will be used.

Adverse events of special interest and SAEs of special interest will be presented by risk and preferred term and will also be analyzed for the following selected subgroups:

- Age group (12 to 17 years, \geq 18 years)
- Sex (male, female)
- Pre-bronchodilator FEV₁ in % of predicted FEV₁ at run-in visit 101 (50% to < 60%, 60% to < 85%)

All deaths in the clinical database will be listed with both the investigator-reported principal cause and the adjudicated primary cause presented side by side. If adverse events (including asthma exacerbations) leading to death start between the first dose and the last dose + 30 days, then those deaths will be included in summary tables. The adjudicated primary cause of death will be summarized with pre-defined categories (cardiovascular, respiratory, cancer, other, intermediate causes) and subcategory.

In addition, time to event analyses will be done for the following endpoints:

- adverse event by the 5 most frequent preferred terms,
- serious adverse event (if there are more than 10% of patients with at least one SAE)
- adverse event of special interest by risk category (if there are more than 10% of patients with events in the respective risk category)
- adjudicated serious asthma outcome (composite endpoint and by single component – if there are more than 10% of patients with events)

The adverse event onset date will be considered as the date of event. Patients who did not experience the event of interest will be taken as censored. For those patients who either completed or discontinued study treatment, the censoring time will be the minimum of (the last treatment day + 30 days, day of death, day of follow-up day Visit 301). For patients who are ongoing at the time of interim database freeze, the DLP date will be used for censoring.

For the legal requirements of ClinicalTrials.gov and EudraCT, two required tables on treatment emergent adverse events which are not serious adverse events with an incidence greater than 3% and on treatment emergent serious adverse events and SAE suspected to be related to study treatment will be provided by system organ class and preferred term on the safety set.

If for a same patient, several consecutive AEs (irrespective of study treatment causality, seriousness and severity) occurred with the same SOC and PT:

- a single occurrence will be counted if there is ≤ 1 day gap between the end date of the preceding AE and the start date of the consecutive AE
- more than one occurrence will be counted if there is > 1 day gap between the end date of the preceding AE and the start date of the consecutive AE

For occurrence, the presence of at least one SAE / SAE suspected to be related to study treatment / non SAE has to be checked in a block e.g., among AE's in a ≤ 1 day gap block, if at least one SAE is occurring, then one occurrence is calculated for that SAE.

The number of deaths resulting from SAEs suspected to be related to study treatment and SAEs irrespective of study treatment relationship will be provided by SOC and PT.

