2.4 Study medication

2.4.1 Duration of exposure

Duration of exposure to study treatment will be calculated as the number of days starting from the first dose date up to and inclusive the last dose date (ignoring the duration when study treatment may have been interrupted). The duration of exposure will be summarized by treatment for the safety set as a continuous variable with the standard descriptive statistics. In addition, the duration of exposure will be summarized with total patient years and the number (%) of patients who were exposed to study drug for each 1 - 29 days, 30 – 86 days, 87 – 183 days, 184 – 254 days, 255 – 365 days, and > 365 days.

In the interim analysis, patients who are ongoing at the time of interim database freeze will be considered as exposed until the DLP.

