For **diary data (PEF, symptom scores and rescue medication use)**, post-baseline measurements start with the morning recordings at Day 2 and end with the evening recordings one day after the last evening dose. Summary data (i.e., mean values and percentage of days with) will be calculated for 4-weekly intervals (defined as 28 days), for Weeks 1 – 26 (defined up to Visit 207, Day 183), and for Weeks 1 – 52 (defined as the whole treatment period up to Visit 214, Day 365). Similar calculations as for baseline diary data will be done. If there will be less than 14 days with data in a 4-week period, then the data should collapse with the previous 4-week period. For Weeks 1 – 26 and 1 – 52, summary values will only be calculated if a patient has at least 30% of their diary days and at least 20 diary days with evaluable data for that variable in the period of interest.

For **safety data**, post-baseline measurements comprise recordings up to the last dose of study drug + 7 days for laboratory, ECG, vital signs, non-serious AE and up to the last dose of study drug + 30 days for SAEs and death. ECG, vital signs and laboratory values which have complete date and time values are assigned to pre or post-dose assessment based on the actual date/time. However, values with missing date/time are assigned to their respective scheduled visit date and time given the visit number and time point are non-missing. If a measurement scheduled as

pre-dose is actually performed post-dose, or vice versa, the data will not be used for by time point assessments but will be included in the summaries of the notable values and extreme values.

When change from baseline is of interest the following formula will be used for each scheduled visit and time-point where baseline and post-baseline values are both available:

Change from baseline = post-baseline value – baseline value.

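### AE incidence rates count events up to 7 or 30 days after last dose but give event-free patients risk time only to last dose; the event window for non-serious AEs in the time-to-event analyses is also not settled

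*SAP*

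**What the plan says.** **Event window.** SAP 2.7.2 says that, in general, AE summaries include events starting from first dose "but not later than 7 days (30 days in the case of a serious adverse event, SAE) after the last administration". SAP 16.1.9.3.3 repeats this for safety data: "post-baseline measurements comprise recordings up to the last dose of study drug + 7 days for laboratory, ECG, vital signs, non-serious AE", with 30 days for SAEs and death.

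**Rate denominator.** For the incidence rate per 100 patient-years, SAP 2.7.2 lets a patient who has the event contribute time until its first occurrence. Everyone else falls under a second rule: "patients without the event of interest will be counted with their full exposure", with a reference to SAP 2.4.1. That section defines exposure as "the number of days starting from the first dose date up to and inclusive the last dose date". At the interim, ongoing patients are treated as exposed to the DLP.

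**Time-to-event censoring.** For patients who completed or discontinued treatment, SAP 2.7.2 sets one rule for all AE endpoints: "the censoring time will be the minimum of (the last treatment day + 30 days, day of death, day of follow-up day Visit 301". Ongoing patients are censored at the DLP. The endpoints are the five most frequent preferred terms and, subject to a 10% threshold, SAEs, AEs of special interest by risk category, and adjudicated serious asthma outcomes.

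**The concern.** A person-time rate is interpretable only if every day on which an event could be counted is also in the denominator. Here a non-serious AE on day 5 after last dose, or an SAE on day 20, enters the numerator, but an event-free patient contributes nothing after last dose. The relative error grows as exposure shortens. SAP 2.7.2 introduces these rates to control for exposure differences between arms, so the error depends on the very imbalance they are meant to remove.

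The time-to-event rule raises a related question. Thirty days fits SAEs, but the frequent preferred terms and AEs of special interest also include non-serious events, for which another part of the SAP closes the window at 7 days.

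The SAP already matches the two elsewhere. Exacerbations count to one day after last dose, censoring uses last treatment plus one day (both SAP 2.6.2.7), and time at risk is exposure plus one day (SAP 16.1.9.6).

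**Working it through.** The documents state no AE rate or event count, so there is no figure to reproduce. The check compares definitions and then sizes the gap.

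**Inputs from the documents.** Event window: last dose + 7 days, or + 30 days if serious (SAP 2.7.2, 16.1.9.3.3). Exposure *T*: first to last dose inclusive (SAP 2.4.1). Completer: *T* = 365 (Protocol 5.4.4 puts the last dose on Day 365). Censoring: last treatment day + 30 (SAP 2.7.2).

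**Per event-free patient no longer on treatment.** Missing denominator time is 7/*T* (non-serious) or 30/*T* (serious). If the 7-day limit governs the time-to-event analyses, surplus risk time is 30 − 7 = 23 days, or 23/(*T* + 7).

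| *T* (days) | 7/*T* | 30/*T* | 23/(*T* + 7) |
|---|---|---|---|
| 365 | 1.9% | 8.2% | 6.2% |
| 183 | 3.8% | 16.4% | 12.1% |
| 86 | 8.1% | 34.9% | 24.7% |

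The 183- and 86-day rows describe early discontinuers only. A patient ongoing at the DLP has neither shortfall nor surplus.

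**Arm level, rates (simulation; assumptions not from the documents).** Constant hazard, the same on and shortly after treatment: 30 per 100 patient-years for a non-serious AE, 8 for an SAE. Early discontinuation of 5% to 30%, uniform over the year.

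- Non-serious: the SAP rule gives 30.477 (5% discontinuation) to 30.575 (30%), against 29.971 and 29.976 with a matched denominator. Ratios: 30.477/29.971 = 1.017 and 30.575/29.976 = 1.020.
- Serious: 8.638 to 8.739, against 7.994 and 7.995. Ratios: 8.638/7.994 = 1.081 and 8.739/7.995 = 1.093.
- Between arms with equal true rates, at 30% against 5% discontinuation: 30.575/30.477 = 1.003 (non-serious) and 8.739/8.638 = 1.012 (serious).

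Stopping the clock at last dose for patients with a post-dose event changes almost nothing (30.495 against 30.494 at 10% discontinuation). The gap comes from the event-free patients.

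**Arm level, time to event (same 30 per 100 patient-years, true hazard ratio 1, events counted to + 7 days).** Censoring at + 7 against + 30 days:

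| Discontinuation, arm A vs B | Day 365 incidence in A, + 7 / + 30 | Hazard ratio, + 7 / + 30 | Shift |
|---|---|---|---|
| 10% vs 10% | 25.9% / 25.8% | 1.0048 / 1.0048 | 0.0% |
| 20% vs 10% | 25.9% / 25.7% | 1.0047 / 0.9978 | 0.7% |
| 30% vs 10% | 25.9% / 25.5% | 1.0041 / 0.9897 | 1.4% |
| 30% vs 5% | 25.9% / 25.5% | 1.0038 / 0.9862 | 1.8% |

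**The case against.** The strongest reply concerns the time-to-event analyses. A reader might infer that the SAP definitely keeps patients at risk too long there, so that the two rules err in opposite directions. The documents do not go that far. The 7/30-day limit in SAP 2.7.2 is stated for summaries in general, and the time-to-event paragraphs set no 7-day limit. Protocol 5.4.9 collects AEs as well as SAEs to 30 days after stopping, and the treatment-emergent definition in Protocol 9.5.2 has no upper bound. Counting all AEs to 30 days is a coherent reading with no mismatch. SAP 16.1.9.3.3 points the other way. What stands is that the window is unsettled.

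A reader might also take 23 surplus days to apply to every patient, or the 183-day percentages to describe an arm or the interim. Neither follows. The 23 days are a maximum, for event-free patients who have stopped or completed treatment; they exclude patients censored at the DLP and shrink with earlier death or Visit 301. For completers they fall after about Day 372, where few events remain to be compared, so they hardly affect a Cox estimate or the incidence to Day 365. Patients ongoing near Day 183 at the interim are exposed to the DLP and lose nothing.

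It is also fair to say that these analyses lie outside the confirmatory family, that crude counts and percentages are reported alongside, and that several time-to-event analyses run only above a 10% event threshold. Censoring at 30 days already fits SAEs and serious asthma outcomes. None of this repairs the rate denominator.

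**Conclusion.** The rate problem holds on the text, and nothing elsewhere in the documents cures it. Absolute rates will be overstated by about 2% for non-serious AEs and 8-9% for SAEs, assuming constant hazards that continue unchanged after last dose and 5% to 30% early discontinuation. A hazard that changes after stopping would give other figures. Between-arm comparisons are much less affected, because the error is nearly common to all arms unless discontinuation differs.

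The time-to-event point is a conditional one: a surplus arises only if the 7-day limit applies, and its effect was then under 2% on the hazard ratio in the scenarios tried.

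Because ongoing patients carry no mismatch, the size of the rate error can differ between the two study reports for purely definitional reasons. The point is minor: it concerns safety reporting and leaves the primary and key secondary analyses untouched.

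**What to change.** For each AE endpoint, use one window for event counting, rate denominator and censoring: first dose to min(last dose + W, death, last contact, DLP).

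- SAEs, fatal events and serious asthma outcomes: W = 30 days.
- Endpoints restricted to non-serious AEs: W = 7 days.
- Endpoints that mix the two (all AEs, preferred terms, AEs of special interest): state one W for the rate and time-to-event analyses and apply it to every event in the endpoint. Thirty days is a workable choice, since AEs are collected that long. A flat 7 days would drop serious events on days 8 to 30 that SAP 2.7.2 now counts.

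The cost is a short paragraph in SAP 2.7.2, a consistent line in 16.1.9.3.3 and a programming change to the time-at-risk derivation. No new data are needed. The drawback is that, for mixed endpoints, the events in these analyses may differ slightly from those in the crude treatment-emergent tables; a footnote can explain this.
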